8.2 Statistical Methods

The primary study endpoints, WOMAC and VAS scores, will be collected at baseline, 1 month follow-up, 3 month follow-up, and 6 month follow-up. Mean WOMAC and VAS scores will be reported at baseline, 1 month follow-up, 3 month follow-up, and 6 month follow-up, along with associated confidence intervals.

We will address the primary study endpoints by modeling each clinical outcome using random coefficient modeling. The clinical outcomes will be modeled as a linear function of time. We will allow a random intercept and slope that is dependent on treatment, so that each patient will have their own trajectory of pain over time. No additional covariates will be included in the model. We will employ a compound symmetric R-side covariance structure to account for dependencies arising from observations from the same patient. Random coefficient models are robust to missing values only require data to be MAR (and not the stronger assumption of MCAR), so that presence of missing values will not invalidate our conclusions.

We will compute predicted means, as well as the estimated difference in predicted means, at 6 months for both WOMAC and VAS; these will be derived from the population-averaged trajectories (i.e. fixed effects). We will test the H₀: $\mu_{sham, 6}$ months - $\mu_{GAE, 6 \text{ months}} = 0$ versus the one-sided alternative hypothesis H_a: $\mu_{sham, 6}$ months - $\mu_{GAE, 6 \text{ months}} > 0$ using a Wald test. Both primary study endpoints will be evaluated by considering significance of the p-value (p < 0.05) along with the percentage predicted mean difference with respect to the clinically relevant differences (16% for WOMAC and 15% for VAS). Both these factors will be taken in tandem as evidence to suggest GAE treatment efficacy. Primary endpoints will be assessed only at one time point, so that adjustment for multiple comparisons is not necessary since the evaluation of the primary endpoints for WOMAC and VAS each consists of only one statistical test. Non-significance of the p-value for this test will be considered inconclusive evidence against the null hypothesis. Variance components, including the intraclass correlation coefficient, will also be reported for each model. All analyses will use SAS version 9.4 (SAS Institute, Inc., Cary, NC).

We will identify extreme primary endpoint values by computing studentized residuals and then conduct sensitivity analyses by deleting these outliers from the analysis datasets. We will repeat the above statistical tests and use results of the sensitivity analyses to corroborate conclusions reached in the primary analyses.

We will address the secondary study endpoint of reduction of OA by comparing frequency of OA medical therapy between the sham group, the crossover group, and the GAE group at 12 months. We will employ a chi-squared test to test the H_0 : frequency of OA medical therapy is equal for between the sham group, the crossover group, and the GAE group versus the one-sided alternative hypothesis. A p-value of < 0.05 will be taken as evidence to suggest that the frequency of OA medical between the groups. Non-significance of the p-value for this test will be considered inconclusive evidence against the null hypothesis.

Reduction in AE will be evaluated with a multilevel logistic regression model. The outcome of adverse events will be regressed on treatment status. We will employ a compound symmetric R-side covariance structure to account for dependencies arising from observations from the same patient. The H_0 : frequency of AE is equal for between the sham group and the GAE group will be assessed versus the two-sided alternative hypothesis with a statistical test of the treatment

parameter different than 0, with a p-value of < 0.05 taken as evidence to suggest that the frequency of OA medical therapy is not equal between the groups. Non-significance of the p-value for this test will be considered inconclusive evidence against the null hypothesis.

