3.1 General Design

This will be a single-blinded randomized-controlled study of GAE versus placebo in a small population with knee pain secondary to arthritis to determine safety and efficacy. After IRB approval of a written informed consent and over, approximately a 24 month duration, N=21 subjects will be recruited. Only subjects ≥ 40 years will be screened for study recruitment. Subjects will be randomized in a 2:1 ratio of GAE:Placebo and will be blinded from study treatment (see flow chart below). The placebo procedure will be a diagnostic angiogram of the knee, without embolization. Appropriate measures will be taken to ensure patients and nursing staff caring for the patient are blinded to assignment. Each patient will be told at the time of recruitment that they may be randomly assigned to sham, but if after 1 month they have not had symptom improvement, their assigned procedure would be revealed and, if they had undergone a sham procedure, they will be allowed to proceed with embolization. This second procedure should be shorter than a complete angiogram and embolization, as the detailed angiogram will not need to be repeated, and therefore both arms will have similar total radiation dose.

Clinical procedures and evaluations will consist of a preoperative screening assessment to determine if the potential study subject meets the inclusion and exclusion criteria, enrollment, surgical procedure for geniculate artery embolization, and follow-up visits at 24 hours, 2 weeks, 1, 3, 6, & 12 months. An MRI will be performed after the 1-month visit in those patients who underwent embolization to detect a change in synovial vascularity and to exclude complication.

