4.2 Anticipated Number of Research Subjects

Enrollment into the investigation will be defined as providing informed consent for study participation per IRB policies.

Twenty-one (21) subjects will be enrolled and all are anticipated to complete the study.

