6.1 Screening Visit (Visit 1)

Potential enrollees will first be identified and will undergo a standard knee OA work-up to include history and physical exam with emphasis on specific site of knee tenderness. The Western Ontario and McMaster University Osteoarthritis Index (WOMAC) questionnaire will be administered to assess difficulty as a result of pain, stiffness and overall decreased function secondary to knee pain in the past week.

Current pain will also be assessed using a visual analog scale (VAS). A knee radiograph will be obtained and evaluated using the Kellgren-Lawrence grading scale. A baseline knee MRI will also be acquired to evaluate for concomitant pathology as part of routine orthopedic evaluation. If the patient previously had an MRI for clinical care that can be obtained from his/her medical record and used for the purposes of this study.

If a patient qualifies to be a subject in the study based on the inclusion and exclusion criteria listed in section 4.3 and 4.4, the local study coordinator, investigator or designee will provide the candidate with a copy of the approved informed consent. Written informed consent will be obtained if appropriate. If the patient wishes to take more time to review the study before enrolling, he/she may complete the consent process at the beginning of the next visit, prior to the study GAE procedure. Those candidates who are disqualified from study entry will be logged into the Screening Log with a reason for no study entry. A copy of the consent will be provided to the subject and the original filed in the study files.

Patients will be randomized at this point according to the schema created prior to the commencement of the study.

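### As most plainly read, section 8.2 compares 6-month means without adjusting for baseline, so chance imbalance between 14 and 7 subjects costs precision that adjustment could recover if baseline and follow-up are moderately correlated.

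*Combined protocol and SAP*

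**What the plan says.** Section 3.1 states that "N=21 subjects will be recruited" and that "Subjects will be randomized in a 2:1 ratio of GAE:Placebo", which gives 14 and 7. Section 4.2 assumes no loss: "Twenty-one (21) subjects will be enrolled and all are anticipated to complete the study".

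Section 8.2 lists baseline with months 1, 3 and 6 as the times of the modelled outcomes, and makes each outcome linear in time. On the model terms it says "We will allow a random intercept and slope that is dependent on treatment", and then "No additional covariates will be included in the model". The tested quantity is the sham-minus-GAE difference in 6-month means predicted from the fixed effects, "versus the one-sided alternative hypothesis", with success judged by "considering significance of the p-value (p < 0.05") together with the percentage difference read against 16% (WOMAC) and 15% (VAS).

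Baseline scores are available for both scales. Section 6.1 has the WOMAC administered at screening and adds "Current pain will also be assessed using a visual analog scale (VAS"). The text on randomisation (5.2, 6.1, 10.3) mentions no stratification by baseline score. Section 8.1 states power of at least 69.1% (WOMAC) and 51.7% (VAS).

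**The concern.** If each arm has its own intercept, then with complete data each arm's 6-month mean is estimated from that arm's own observations alone. Randomisation makes the true baseline difference zero, but the model does not use that fact. With only 7 sham subjects the observed baseline means can differ noticeably, and the part of that difference that persists to 6 months stays in the contrast. It then affects both the p-value and the point estimate that is read against 16% and 15%.

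The stated power is modest, particularly for VAS. Adjusting for a score that is already collected is one of the few ways to gain precision without more patients or visits.

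**Working it through.** **Inputs.** From 8.1: WOMAC mean 12.2, SD 1.9; VAS mean 72, SD 13.3. From 3.1: 14 v 7. From 8.2: one-sided 0.05; visits at 0, 1, 3 and 6 months; linear trend. Targets: 0.16 × 12.2 = 1.952 points; 0.15 × 72 = 10.8 mm. Assumed, because the documents give none: the correlation ρ between any two visits (compound symmetry), from 0.2 to 0.7. As in 8.1, the baseline SD is used at 6 months. Data are taken as complete.

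**Power formula.** Power = P(T > t(0.95, df)), where T is noncentral t with noncentrality target / [SD × √(v × (1/14 + 1/7))]. Here v is the variance of the 6-month contrast relative to a single 6-month visit, and 1/14 + 1/7 = 0.2143.

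**1. The plan's own figures.** With v = 1 and df = 19, power is 68.9% (WOMAC) and 51.9% (VAS), against the stated 69.1% and 51.7%. They reproduce.

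**2. Planned model (separate intercepts, df 19).** The straight-line prediction at month 6 weights the four visits −1/6, 0, 1/3, 5/6. The squared weights sum to 5/6, so v = (1 − ρ) × 5/6 + ρ. At ρ = 0.5, v = 0.417 + 0.500 = 0.917.

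**3. How much imbalance reaches the tested difference.** The SE of the baseline difference is SD × √0.2143: 1.9 × 0.463 = 0.880 points and 13.3 × 0.463 = 6.157 mm. The fraction carried to the 6-month contrast is −1/6 + ρ(1/3 + 5/6) = 1.167ρ − 0.167, which is 0.18 at ρ = 0.3, 0.42 at 0.5 and 0.65 at 0.7. At ρ = 0.5 a one-SE imbalance shifts the contrast by
- WOMAC: 0.417 × 0.880 = 0.37 points (0.37/1.952 = 19% of target)
- VAS: 0.417 × 6.157 = 2.6 mm (2.57/10.8 = 24% of target)

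**4. Common baseline mean (df 18).** The fixed effects are intercept, time and treatment × time. Generalised least squares gives v = 0.860, 0.834, 0.692 and 0.461 at ρ = 0.2, 0.3, 0.5 and 0.7.

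**5. Baseline as covariate (df 18).** Months 1, 3 and 6 are the outcomes, with arm-specific level and linear trend. The weights at month 6 are −3/19, 5/19, 17/19, whose squares sum to 17/19. Given baseline, v = [(1 − ρ) × 17/19 + ρ(1 − ρ)] × (1 + 1/17), where the last factor is the expected cost of estimating the covariate slope with 21 subjects. At ρ = 0.5, v = (0.447 + 0.250) × 1.059 = 0.738.

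**Power, %**

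| ρ | WOMAC planned | common baseline | covariate | VAS planned | common baseline | covariate |
|---|---|---|---|---|---|---|
| 0.2 | 74.3 | 74.5 | 71.6 | 56.8 | 57.0 | 54.3 |
| 0.3 | 73.6 | 75.6 | 73.4 | 56.1 | 58.0 | 55.9 |
| 0.5 | 72.2 | 82.1 | 79.9 | 54.8 | 64.9 | 62.5 |
| 0.7 | 70.9 | 93.3 | 91.2 | 53.6 | 79.9 | 76.6 |

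**6. Sensitivity.** Section 8.2 also names random slopes. With random intercept and slope (intercept variance share 0.4 to 0.8, slope SD 0.05 to 0.15 baseline SDs per month, intercept-slope correlation −0.3 or 0), the gain from a common baseline mean ran from under 1 point to over 30. The direction held throughout; the size did not.

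**The case against.** **The wording is ambiguous.** The treatment clause in 8.2 can be read as applying to the slope only. The model would then already have one baseline mean for both arms, and the loss would not arise. This stands as a limit on certainty. It also shows that the fixed effects need writing out, since at ρ = 0.5 the two readings differ by about 10 power points.

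**The gain is not assured.** It depends on a correlation the documents do not give. At ρ = 0.2 the covariate form loses 2.7 points (WOMAC) and 2.5 (VAS), and at 0.3 it gains nothing. The entry requirement of VAS above 50 mm (4.3) restricts the range and tends to lower that correlation for VAS. All of this stands.

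**Stronger readings that fail.** A reader might infer that the test is biased or its type I error inflated. It is not: over repeated randomisations the planned contrast is unbiased, and an unadjusted prespecified model is legitimate. A reader might also take the raw baseline SE, 45% of the WOMAC target (0.880/1.952) and 57% of the VAS target (6.157/10.8), as the error in the result. Only the carried fraction from step 3 matters. At ρ = 0.5 the carried shift exceeds half the target in about 0.8% (WOMAC) and 3.5% (VAS) of trials; at 0.7, in about 9% and 18%. Nor is the baseline score wholly unused: as an outcome row it helps fit each trajectory and supports the likelihood when later visits are missing.

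**Crossover may matter more.** Unimproved sham subjects may be unblinded and cross over after 1 month (5.2, 6.5), leaving fewer than 7 sham subjects at 6 months. That is a separate issue, which these figures ignore. It does not remove this one.

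**Conclusion.** The point holds as one of efficiency and specification. On the plain reading of 8.2 the tested 6-month difference is not baseline-adjusted. The cost of this, relative to a common baseline mean, is negligible at correlation 0.2, about 2 power points at 0.3, about 10 at 0.5, and about 22 (WOMAC) and 26 (VAS) at 0.7. For a given trial it also means that the estimate moves with whatever imbalance occurred.

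These sizes rest on compound symmetry, complete data, 7 sham subjects at 6 months, the baseline SDs of 8.1 and an assumed correlation. The change is worth making because the possible gain is much larger than the possible loss, but no single power gain should be promised.

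**What to change.** In 8.2, replace the sentence that bars covariates and write out the fixed effects so that baseline is adjusted for, in one of two ways:

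- **Common baseline mean.** Keep baseline as an outcome and constrain both arms to one baseline mean. There was no material power loss at any correlation tried. With a linear trend, however, this forces the treatment-effect line through zero at baseline.
- **Baseline as covariate.** Use the baseline value of the same scale as a covariate, with months 1, 3 and 6 as outcomes. This avoids that constraint, at the price of one degree of freedom and a small power loss if the correlation is below about 0.3.

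Under either form, test the baseline-adjusted sham-minus-GAE difference at 6 months. State the form of the time trend, and the denominator that turns the adjusted difference into a percentage for the 16% and 15% comparisons. The same edit settles whether the intercept depends on treatment.

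The cost is a few sentences in 8.2, with no new patients, visits or data. The choice should be fixed before unblinded outcomes are seen.

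### The primary model includes both a random intercept and a compound-symmetric residual covariance; only their sum can be estimated, so the promised variance components and an undefined ICC have no unique value

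*Combined protocol and SAP*

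**What the plan says.** Section 8.2 (Statistical Methods) describes one model per outcome: "We will address the primary study endpoints by modeling each clinical outcome using random coefficient modeling". Three statements fix its form.

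- Mean: "The clinical outcomes will be modeled as a linear function of time". The scores "will be collected at baseline, 1 month follow-up, 3 month follow-up, and 6 month follow-up".
- Patient-level random effects: "We will allow a random intercept and slope that is dependent on treatment".
- Residual covariance: "We will employ a compound symmetric R-side covariance structure to account for dependencies arising from observations from the same patient".

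The section then commits to an output: "Variance components, including the intraclass correlation coefficient, will also be reported for each model". It gives no ICC formula or time point. It names SAS 9.4 but no procedure or code, puts no constraint on either covariance term, and gives no fallback if the model cannot be fitted. The 6-month treatment difference is taken from the fixed effects and tested one-sided with a Wald test at 0.05.

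**The concern.** A random intercept and a compound-symmetric residual matrix are two ways of writing the same thing: a constant covariance between any two visits of one patient. With both in the model, the likelihood is flat along the direction that trades one against the other.

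Two things are at stake. First, part of the promised output is undefined: the intercept variance, the compound-symmetry covariance, and any ICC that uses one without the other. Second, software facing a singular information matrix may fail to converge, warn about the Hessian, or set a term to zero. Someone must then decide which term to remove, possibly after seeing the data, and the plan does not say which. Some of the available repairs change the SE of the primary test.

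**Working it through.** **Inputs from the documents.** Visits at 0, 1, 3 and 6 months, linear time, and both covariance structures (section 8.2); 21 patients (section 4.2) allocated 2:1 (section 5.2), so 14 GAE and 7 sham. The documents give no variance components for this model. Those used in steps 3 to 5 are assumptions; steps 1 and 2 need none.

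**The plan's own figures.** Section 8.1 states power of 69.1% (WOMAC) and 51.7% (VAS). A one-sided two-sample t-test at 0.05 with 14 v 7 gives 68.95% (d = 0.16 × 12.2 / 1.9 = 1.027) and 51.85% (d = 0.15 × 72 / 13.3 = 0.812). The stated power therefore reproduces from a t-test and does not depend on the covariance model.

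**Step 1. Marginal covariance.** With Z = [1, t], J the 4 × 4 all-ones matrix and I the identity:

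V = Z G Z′ + cs·J + s2·I, where G holds g11 (intercept variance), g12 (intercept–slope covariance) and g22 (slope variance).

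For visits at times t and u, the off-diagonal element is g11 + (t + u)·g12 + t·u·g22 + cs. On the diagonal, s2 is added. So g11 and cs appear only as g11 + cs.

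**Step 2. Rank.** ∂V/∂g11 = J and ∂V/∂cs = J. The five parameters have rank 4, and the null direction is g11 up, cs down by the same amount. The Fisher information has one zero eigenvalue, whatever the data. If the treatment dependence is read as arm-specific covariance, the redundancy remains: rank 6 of 7 (R by arm), 7 of 8 (G by arm), 8 of 10 (both). Without cs, rank is 4 of 4. With the random intercept dropped and slope plus compound symmetry kept, rank is 3 of 3.

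**Step 3. Illustration.** One simulated WOMAC data set, 14 v 7, assumed variances. The REML fit without cs gave g11 = 2.835, g12 = 0.004, g22 = 0.061, s2 = 0.717. Moving part of g11 into cs:

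| Share moved | g11 | cs | −2 REML logL | Difference (SE), z | g11/(g11+cs+s2) | (g11+cs)/(g11+cs+s2) |
|---|---|---|---|---|---|---|
| 0% | 2.835 | 0 | 145.3466 | 1.902 (1.102), 1.726 | 0.80 | 0.80 |
| 25% | 2.126 | 0.709 | 145.3466 | same | 0.60 | 0.80 |
| 50% | 1.418 | 1.418 | 145.3466 | same | 0.40 | 0.80 |
| 75% | 0.709 | 2.126 | 145.3466 | same | 0.20 | 0.80 |
| 90% | 0.284 | 2.552 | 145.3466 | same | 0.08 | 0.80 |

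**Step 4. ICC and time.** Even an ICC built on the sum varies with time when slopes are random. At baseline it is 2.835/(2.835 + 0.717) = 0.80. At 6 months the patient-level variance is 2.835 + 12 × 0.004 + 36 × 0.061 ≈ 5.07, and 5.07/(5.07 + 0.717) = 0.88.

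**Step 5. An unplanned repair.** Suppose the random slope is dropped and compound symmetry alone is kept. Assume intercept SD 9, residual SD 9, no intercept–slope covariance and complete data. The SE of the 6-month difference is then:

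| Assumed slope SD (points/month) | SE reported by the compound-symmetry model | True SE | Ratio |
|---|---|---|---|
| 1 | 5.83 | 6.29 | 0.93 |
| 2 | 6.38 | 7.92 | 0.81 |
| 3 | 7.19 | 10.06 | 0.71 |

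Simulation under the same SDs (150 data sets each, so imprecise) gave one-sided type I error of 5.3%, 9.3% and 14.0% for compound symmetry alone, against 2.7%, 4.7% and 5.3% for random intercept and slope with independent residuals.

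**The case against.** The strongest reply is that the redundancy does not touch the primary result. V itself is identified, and the 6-month difference, its SE and its Wald z depend on V alone; step 3 shows them constant. This stands, and it is why the point is not critical.

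The reply also holds on the ICC: compound-symmetry covariance is within-patient covariance, and an ICC with g11 + cs in the numerator is stable at a given time. But the plan does not say that this is the ICC it means, and the value still moves with time. The ICC is descriptive and no decision rests on it.

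Three stronger readings are tempting and are not supported.

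- A reader might infer that no variance component is identified. Only the split between g11 and cs is lost; the slope variance, the intercept–slope covariance, the residual variance and the sum g11 + cs are all estimable.
- A reader might infer that small-sample degrees of freedom become arbitrary. The plan names a Wald test and no such method. In a check with assumed intercept variance 87, residual 87, slope variance 3 and covariance 2, the SE was 7.903 and the Satterthwaite df 19.0 (by generalised inverse) at every split, as in the model without cs. Software might refuse a singular matrix, but the answer is not arbitrary.
- A reader might infer that the adverse-event model has the same fault, since section 8.2 says "Reduction in AE will be evaluated with a multilevel logistic regression model" and repeats the compound-symmetry sentence. No random intercept is named there, and in a logistic model a random effect acts on the link scale, so the algebra above does not carry over. That model is loosely described, not shown to be unidentifiable.

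Finally, no SAS fit was run and no code is given, so a convergence failure is a risk, not a prediction.

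**Conclusion.** The point holds in limited form. As written, the primary covariance model has one parameter too many: five parameters, rank 4, singular information. This follows from the wording alone and needs no assumed variances. The split between intercept variance and compound-symmetry covariance, and any ICC built on the intercept variance alone, have no unique value.

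The 6-month estimate, SE and test are unaffected if the software converges. The practical exposure is an unplanned repair. Removing either the compound symmetry or the random intercept restores identifiability. Removing the random slope and keeping compound symmetry understates the SE when slopes vary: by 7%, 19% and 29% (one minus the ratios in step 5) for slope SDs of 1, 2 and 3. Those sizes rest on assumed variances and would shrink towards zero if patients' slopes hardly differ.

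Severity is moderate: a specification error to correct before the data are analysed, not one that invalidates the primary test.

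**What to change.** 1. Delete the compound-symmetry sentence from the primary-model paragraph of section 8.2. State that the model has a random intercept and slope with independent residuals (four covariance parameters, all identified).
2. State whether the treatment dependence refers to the fixed intercepts and slopes or to arm-specific covariance matrices.
3. Define the ICC by formula and time point, or report the estimated between-visit correlations in its place.
4. Pre-specify what is done if the estimated G matrix is not positive definite, including the trigger. If the fallback is a random intercept only, say that it is equivalent to compound symmetry (for non-negative covariance) and may be anticonservative, and label its result accordingly.

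The cost is SAP wording only. No change to data collection, sample size or stated power is needed.

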5.2 Method for Assigning Subject to Treatment Groups

Subjects who meet all criteria for study entry and have signed written informed consent will be randomized in a 2:1 allocation of treatment (geniculate artery embolization) versus placebo (angiogram). Patients will be blinded to the study procedure. Each patient will be told at the time of recruitment that they may be

randomly assigned to GAE or sham. If after 1 month if they have not had symptom improvement, their assigned procedure would be revealed only if they had undergone a sham procedure. They will then be allowed to proceed with embolization in Arm C if they elect to proceed. This second procedure should be shorter than a complete angiogram and embolization, as the detailed angiogram will not need to be repeated. See table 1 (study schema). A 2:1 ratio was selected so that patients would be more likely to enroll in the study.

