6.5 Visit 5a and 5b - 1 Month Follow-Up

Subjects will be seen in clinic or contacted by phone or by teleconference, per the subject's preference, 30 +/- 7 days following GAE or sham procedure. The WOMAC questionnaire and VAS pain score will be completed and subjects will be evaluated for possible adverse events. An MRI of the treated knee will be acquired for those subjects who underwent GAE*. Subjects will also provide an update about the necessity/frequency of pre-established conservative therapies.

For those subjects who do not report improvement in symptoms or worsening, and are in the placebo arm, they will be unblinded and offered to undergo the geniculate artery embolization (Arm C) and then followed at similar follow-up intervals to 12 months (24 hours, 2 weeks, 1 month, 3 months, 6 months, and 12 months).

*MRI is only scheduled at one month in order to evaluate for non-target ischemic injury. These types of injuries will become apparent as early as 24 hours after embolization. Infarcted tissue will still be detectable at one month. Based on our experience with embolization in other areas, it is thought extremely unlikely that new ischemic injury related to the procedure will develop after the one-month follow-up. Additionally, findings that would be detected on later scans may be unrelated to the procedure and confound the data.

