6.6 Visit 6a and 6b - 3 Month Follow-Up for blinded subjects

Subjects will be seen in clinic or contacted by phone or by teleconference, per the subject's preference, 90 +/- 10 days following GAE or sham procedure. The WOMAC questionnaire and VAS pain score will be completed and subjects will be evaluated for possible adverse events. Subjects will also provide an update about the necessity/frequency of pre-established conservative therapies. If an AE is suspected based on change in pain scores or functionality, an appropriate

work-up will be performed which may include MRI.

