6.7 Visit 6c - GAE for unblinded subjects

GAE will be performed (as described in part 5.2 above) within 4 weeks of visit 4. Subjects will be given a pager number to reach a physician, 24 hours a day, to report any adverse symptoms and receive medical advice.

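### Both primary tests compare sham with GAE at month 6, but the plan does not say how sham patients who cross over to GAE after month 1 enter the model, so the stated minimum power is not a minimum

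*Combined protocol and SAP*

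**What the plan says.** Section 8.2 makes month 6 the single primary time point: "We will compute predicted means, as well as the estimated difference in predicted means, at 6 months for both WOMAC and VAS". WOMAC and VAS are each modelled as a straight line in time with patient-level intercepts and slopes. Sham minus GAE at month 6 is tested one-sided at 0.05 and read together with the 16% (WOMAC) or 15% (VAS) threshold.

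Crossover is part of the design. A sham patient who has not improved by month 1 learns the assignment and is offered GAE (3.1, 5.2, 6.5). Section 5.2 puts it this way: "They will then be allowed to proceed with embolization in Arm C if they elect to proceed". The month-3 and month-6 visits timed from the first procedure are headed as visits for blinded subjects ("3 Month Follow-Up for blinded subjects" in 6.6; 6.8 is similar). Arm C visits in 6.11 to 6.13 are timed from the second procedure.

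On incomplete data, 8.2 says "Random coefficient models are robust to missing values only require data to be MAR". Section 8.3 counts a patient as evaluable after GAE or sham and gives no rule for a patient who has had both. Two places hint at an answer: 5.5 labels datasets A, B or C, and 8.2 names a crossover group, but only for the 12-month medication comparison. Section 8.1 presents 69.1% (WOMAC) and 51.7% (VAS) as lower bounds on power.

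**The concern.** The primary contrast comes after the point at which sham patients may receive the active procedure, and the sham arm has seven patients. At least four analyses fit the text:

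- keep crossed patients' later scores as sham, with time from the first procedure;
- keep them as sham, with time restarted at the second procedure;
- drop crossed patients from the sham arm;
- keep their baseline and month-1 scores as sham and stop there.

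These answer different questions and give different estimates. Dropping crossed patients, which the A/B/C labels suggest, leaves a sham arm selected on its month-1 outcome, so the comparison is no longer as randomised. If the choice is left until data are seen, it can decide whether the 15% or 16% threshold is met. The power claim is also affected, because it makes no allowance for sham patients lost to crossover.

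**Working it through.** **1. Stated power.** Inputs: 21 patients at 2:1, so 14 v 7 (3.1); WOMAC mean 12.2, SD 1.9; VAS mean 72, SD 13.3 (8.1); one-sided 0.05 (8.2).

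- WOMAC effect: 0.16 × 12.2 = 1.952; 1.952/1.9 = 1.027.
- VAS effect: 0.15 × 72 = 10.8; 10.8/13.3 = 0.812.
- Noncentrality = effect × √(14 × 7/21) = effect × 2.160, giving 2.219 and 1.754 on 19 df.
- Power: 68.9% and 51.9%, against 69.1% and 51.7% stated.

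The stated figures are therefore a two-sample t-test with all seven sham patients intact.

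**2. Calendar.** The month-1 visit falls on day 23-37 (6.5). Assume the second procedure follows within 28 days, so day 23-65. Arm C 3-month scores then fall on day 103-165 (adding 80-100) and 6-month scores on day 193-255 (adding 170-190). The blinded month-6 window is day 170-190 (6.8). Section 6.7 times the procedure "within 4 weeks of visit 4", which is the 2-week call. Read literally, that ends on day 42 and gives day 103-142 and 193-232. Either way, no scheduled Arm C 3- or 6-month score falls in the month-6 window.

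**3. Power for the planned line, with scores stopped at crossover.** Each arm's month-6 variance is c′(ΣX′V⁻¹X)⁻¹c, with c = (1, 6), rows (1, t), t = 0, 1, 3, 6 (0 and 1 only after crossover), and V = SD²[(1−ρ)I + ρJ]. Assumptions: ρ = 0.3-0.7, known covariance, t reference on 19 df.

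- No crossover: the variance is SD²[ρ + 0.833(1−ρ)]/n. At ρ = 0.5 the standard errors (SE) for VAS are 4.81 (sham) and 3.40 (GAE), so the difference has SE 5.89 and noncentrality 10.8/5.89 = 1.83.
- All seven cross: the sham value is 6 × month 1 − 5 × baseline, with variance (61 − 60ρ)SD²/7. At ρ = 0.5 the SE is 13.3 × √(31/7) = 28.0 mm.

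| Sham patients crossing | Sham VAS SE (mm) | VAS power | WOMAC power |
|---|---|---|---|
| 0 | 4.7-4.9 | 54-56% | 71-74% |
| 1 | 5.1 | 52-53% | 69-70% |
| 2 | 5.3-5.5 | 49-50% | 66-67% |
| 4 | 6.1-6.9 | 39-44% | 53-59% |
| 7 | 21.9-33.0 | 9-12% | 11-15% |

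**4. Selection if crossed patients are dropped.** Suppose the least-improved patients cross. At ρ = 0.5 the month-1 change has SD 13.3, and normal order statistics for n = 7 give mean changes of −5.61, −10.92 and −14.02 mm in the 5, 3 or 2 who stay. Under equal correlation, the line's month-6 weights on months 0, 1, 3 and 6 are −1/6, 0, 1/3 and 5/6. The regression of the fitted value on the change is then 1/12, so the sham mean shifts by −0.47, −0.91 and −1.17 mm. If post-baseline visits correlate 0.7 with each other and 0.5 with baseline, and the fit uses that covariance, the shifts are about −0.4, −0.8 and −1.0 mm. If the fit instead uses equal-correlation weights on that pattern, the factor is 0.5/6 + 0.2/3 + 0.2 × 5/6 = 0.317, giving −1.8, −3.5 and −4.4 mm. In every case the sham mean is too low, which works against GAE.

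**5. Estimated VAS difference under the four handlings.** Large-sample fit of the line. Assumptions: true month-6 difference 10.8 mm, effect growing linearly to month 6, no mean change on sham, second procedure at 1.5 months, ρ = 0.3-0.7.

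| Handling | Any month-1 decrease stays (50% cross) | Only a 15% decrease stays (77-87% cross) |
|---|---|---|
| Kept as sham, first clock | 7.0 | 4.2-5.0 |
| Kept as sham, clock restarted | 5.4 | 1.4-2.5 |
| Crossed patients dropped | 9.7-10.1 | 6.5-8.6 |
| Scores stopped at crossover | 10.8 | 10.8-10.9 |

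The last row recovers the true value because MAR holds here by construction.

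**The case against.** The plan's vocabulary points one way: Arm C is a named arm, the datasets are labelled A, B or C, and the medication comparison lists sham and crossover separately. On that reading the primary sham group simply excludes Arm C. This narrows the ambiguity, but it is implied rather than stated, and it is the reading that gives up the randomised comparison.

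A model with continuous time does not need a score inside day 170-190, since Arm C scores on either side could inform the line. That stands. The calendar in step 2 is not itself the defect; the missing arm, time origin and treatment coding are.

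A reader might infer that dropping crossed patients would manufacture a benefit for GAE. The calculations do not support this: the shift works against GAE, and it is small when the fitted covariance is right and two or more sham patients remain.

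A reader might infer that the trial is bound to fall below its stated power, or that month 6 cannot be estimated. The documents give no crossover share and no definition of improvement. With none or one crossing, the planned model roughly matches or exceeds the stated figures.

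A reader might also infer that MAR fails. It is arguable if the offer follows the recorded month-1 scores. The weakness is that improvement is not tied to those scores.

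Finally, the choice of estimand belongs to the sponsor, and it must fit with 5.4, which counts new or escalated therapy after 14 days as treatment failure without saying how failure enters the model. Both points stand; neither supplies the missing rule.

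**Conclusion.** The concern holds. Sections 8.2 and 8.3 leave open whether, in which arm and on which clock post-crossover scores enter both primary analyses, and this must be settled before outcome data are examined. The larger risk is dilution: counting crossed scores as sham cuts a true 10.8 mm to about 7.0 or 5.4 mm at 50% crossover. Dropping crossed patients costs the randomised comparison but moves the sham mean by only about −0.4 to −1.2 mm with 5 to 2 left, or up to −4.4 mm if the fitted covariance is wrong in the way shown. The 69.1% and 51.7% figures are not lower bounds: with scores stopped at crossover, both are passed on the way down once about two of seven sham patients cross. If all seven cross, the sham month-6 value is an extrapolation from baseline and month 1 with SE about 22-33 mm. These sizes rest on assumed crossover counts, correlations of 0.3-0.7 and an effect linear in time. The absence of a rule rests on the documents alone.

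**What to change.** **In 8.2**
- State that the primary analysis is by randomised arm, with time from the first procedure.
- Keep crossover patients' baseline and month-1 scores in the sham arm, and set scores after the second procedure to missing in the primary model.
- Name the estimand: the month-6 difference had no sham patient crossed over, relying on MAR given recorded scores.
- Say what is reported if no sham patient remains.
- Add two sensitivity analyses: one other handling of post-crossover scores, and the baseline-adjusted month-1 comparison of all patients as randomised, with WOMAC and VAS completed before the crossover decision. Sections 3.2 and 7.2 already name month 1 beside month 6.

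**In 8.1**
- Delete the wording that presents the power figures as minimums, and restate power for the planned model over a range of crossover shares.

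**To reconcile**
- Whose assignment is revealed: 3.1 has "their assigned procedure would be revealed and, if they had undergone a sham procedure, they will be allowed to proceed with embolization", while 5.2 has "their assigned procedure would be revealed only if they had undergone a sham procedure".
- The timing of the crossover procedure: 6.7 counts from visit 4, but unblinding happens at the month-1 visit (6.5).

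**Optional**
- Collect WOMAC and VAS by phone at day 170-190 from the first procedure in crossover patients, so that an as-randomised comparison including post-crossover scores is possible. This adds at most seven questionnaires per scale.

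The core change is text only, with no extra patients, visits or procedures. Its price is that the primary result rests on MAR after crossover and loses precision with each crossover.
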